#### **Exclusion criteria:**

- Previous operative procedure for treatment of RLS;
- Current use of TENS (transcutaneous electrical nerve stimulation or plasma exchange;
- Allergy to Cannabidiol (CBD) Cannabidiolic acid (CBDa), or any other ingredient contained in the topical cream;
- Pregnant participants (participants who have the potential for being pregnant will sign a waiver), or breast feeding;
- History of recreational substance abuse, fibromyalgia, Chronic Regional Pain Syndrome (CRPS), psychiatric history including but not limited to schizoaffective disorder, bipolar disorder, chronic depression, and suicidal ideation;
- Conditions affecting capacity and adherence to study regimen including but not limited to dementia/delirium, Alzheimer's, Down's syndrome;
- A need for elective surgery involving preoperative or postoperative analgesics or anesthetics during the study period;
- No recent cannabinoid use in the last 2 months, and no use during the study.

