### Significance:

This technology focuses on the peripheral musculoskeletal component of the Restless Leg Syndrome (RLS), a poorly understood sensorimotor disorder, and is directed at treatment modalities that correct the dysfunction of mechanosensitive channels that contribute to RLS's presumed mechanism of action. Our hypothesis is that modulating activity of the Piezo channels and acting on the TRPA1 that regulate the Piezo channels are key target areas to treat the symptomology of RLS.

Thus, an effective therapeutic agent to treat RLS targeted to the musculoskeletal periphery would be one that possesses three key properties:

- 1. Is amphiphilic enough to effectively penetrate, and consequently modulate, Piezo channel associated membranes.
- Is known to modulate TRPA1.
- 3. Can introduce divalent cations to interfere with the increased calcium flux initiated by overstimulation of Piezo channels.

Chylobinoid is a magnesium infused cannabidiolic acid (CBDa)-rich micellar complex derived from hemp extract. The magnesium CBDa complex is polarity adaptive and that, combined with its micellar structure, imparts the measure of amphiphilicity desired for both relief of membrane tension with distortion of membrane structure and deep penetration through the epidermis to the target site. CBDa is also a potent TRPA1 ligand. Finally, introducing magnesium into the system will contribute to disrupting the calcium flux.

We have already demonstrated, anecdotally, the effectiveness of topically applied Chylobinoid in improving the symptoms associated with RLS. The work described in this protocol is to prove Chylobinoid's effectiveness in treating RLS in a clinical setting.

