### **Research Methods**

**Study design:** Prospective open-label proof-of-concept trial.

**Study Population**: Subjects must meet all of the enrollment criteria to be eligible for this study. Eligibility criteria may not be waived by the Investigator and are subject to review in the event of a Good Clinical Practice audit and/or health regulatory authority inspection.

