## Inclusion criteria:

- Patients with at least 3 month-course of symptomatic restless leg syndrome
- Must meet International Restless Legs Syndrome Study Group (IRLSSG) criteria of at least mild symptoms.
- Age > 18 years, including both males and females
- Patient provides informed consent

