## Participants and protocols:

Participants of both genders will be recruited. Participants with at least a three-month diagnosis of RLS without prior operative intervention will be approached for enrollment in the study. Participants will be enrolled once the trial is described, questions answered, and consent form signed. Pre-treatment IRLSSG scores are collected over the phone on new participant questionnaires. Anyone who does not meet the IRLS criteria for at least mild RLS with a minimum IRLS score of 7 will screen fail. Participants will then have the trial cream described, how to apply it (see below), and then the cream will be mailed to them. Once received, participants will use the cream at least once a night to the affected area(s).

The topical cream will be contained in a jar. The cream will be applied by hand from a measuring spoon and massaged into the skin. The participant will measure 1 teaspoon and apply this amount to each of the regions of the area the participant reports having RLS. Participants will be instructed to apply the topical cream once per day 30-45 minutes before bed for a total duration of two weeks. Participants will be instructed to re-apply the cream if they wake up and feel RLS symptoms.

Participants will receive a follow up phone call at the end of the 2-week study. Post-treatment IRLSSG and the PGIC (patient's global impression of change) will be collected at that time. That completes the study.

Sample Size: 10 participants

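### Do the inverted cannabinoid exclusion item and the two versions of the three-month rule leave it unclear who may enter the trial?

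*Protocol*

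**What the plan says.** Under Exclusion criteria, the protocol lists eight items. Seven name a disqualifying feature, such as earlier surgery for restless legs, an allergy to an ingredient or pregnancy. The eighth is "No recent cannabinoid use in the last 2 months, and no use during the study".

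The Significance section describes the product: "Chylobinoid is a magnesium infused cannabidiolic acid (CBDa)-rich micellar complex derived from hemp extract". Participants and protocols has every participant apply the cream nightly for two weeks.

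The three-month rule appears twice. Inclusion criteria has "Patients with at least 3 month-course of symptomatic restless leg syndrome". Participants and protocols says who will be approached: "Participants with at least a three-month diagnosis of RLS". The latter section also gives the numerical screening cut-off, a minimum IRLS score of 7.

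Research Methods adds that "Eligibility criteria may not be waived by the Investigator" and that the criteria are open to audit and inspection.

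**The concern.** Neither literal reading of the cannabinoid item gives a workable rule. If a person who matches an exclusion item is excluded, then people without recent cannabinoid use are turned away and recent users come in. If the item is instead a requirement, its second half bars all cannabinoid use during the study, and no sentence exempts the cream that everyone is told to use.

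The three-month rule raises a different question. A person with years of symptoms but a recent diagnosis meets the inclusion criterion, yet is outside the group that the recruitment text says will be approached. The protocol does not say which statement governs.

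This could matter because the trial is open-label and has no control group. Its result is a before-after change in 10 people, so another cannabinoid taken at the same time could not be separated from the cream. The cannabinoid item is the only one that addresses ordinary use of such products; the item on recreational substance abuse covers a history of abuse. A rule that cannot be waived ought to be clear.

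**Working it through.** The point turns on wording, and the protocol gives no figure to reproduce. The check is to set the sections side by side.

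**Cannabinoid item: which readings survive?**

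| Reading | What it implies | Fit with the rest of the protocol |
|---|---|---|
| Literal exclusion | Non-users out, recent users in | Fails: the second half would make abstaining during the study a ground for exclusion, which has no sense as an entry rule |
| Ban on every cannabinoid, cream included | Nobody may apply the cream | Fails: Participants and protocols instructs everyone to apply it nightly |
| Washout and abstention from non-study cannabinoids | No use in the prior 2 months; only the study cream during the study | Fits Significance, Exclusion criteria, and Participants and protocols together |

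The same list supports the third reading. Its allergy item names CBD and CBDa alongside the cream's other ingredients, so the authors plainly expected participants to be exposed to them through the cream. The specific instruction to use the cream also takes precedence over a general restriction.

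**How much text is affected?** 8 items − 7 worded as disqualifying features = 1 item worded as a requirement.

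**What would a total ban amount to?** 2 weeks × 7 nights × 1 application = 14 applications per participant, and 14 × 10 participants = 140. That is simply the planned minimum use of the cream. It does not measure bias, or deviations that anyone would record.

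**Three-month rule.** Let S be the time since symptoms began and D the time since diagnosis. The inclusion criterion requires S ≥ 3 months; the recruitment sentence describes people with D ≥ 3 months. Diagnosis ordinarily follows the onset of symptoms, so S ≥ D. There are three cases:

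- D ≥ 3 months: then S ≥ 3 months, and both statements are met.
- S ≥ 3 months but D < 3 months, or no diagnosis yet: the criterion is met, but the person is outside the group described for approach.
- S < 3 months: then D < 3 months, and neither is met.

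No case satisfies the recruitment sentence while failing the criterion. The mismatch can shrink the pool approached but does not ordinarily admit an ineligible person. The protocol gives no basis for counting people in the middle case.

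**Analysis.** The Statistical Analysis Plan section tests the paired change in the rating-scale score by t-test or signed-rank test at alpha 0.05. Neither wording point enters the planned 10 participants, the tests or alpha.

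**The case for a change.** The strongest case for a change rests on the no-waiver clause. If every subject must meet every criterion and an auditor will compare each subject with the text, obvious intent may not be enough: under a ban with no exemption, all 10 participants would be in breach by following instructions. It can also be argued that the recruitment section is more than narrative, since it alone holds the cut-off of 7, and that correcting two or three sentences costs almost nothing.

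Part of this stands. The item is badly phrased, the exemption is not written down, and the two three-month statements differ. But the no-waiver clause forbids exceptions to a criterion. It does not require staff or auditors to choose a reading that contradicts the protocol's own intervention. Reading the item in its only coherent sense is not a waiver.

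The location of the cut-off shows that the recruitment section contains eligibility detail. It does not show that the sentence on who is approached replaces the inclusion criterion. If screeners apply both statements, everyone enrolled still satisfies the criterion.

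Low cost alone is no reason to change the plan when the correction would leave screening, bias, precision, safety and the conclusion as they are.

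**Conclusion.** The concern is accurate about the text but does not call for a change. The cannabinoid item is a clerical slip in 1 of 8 exclusion items, with one workable meaning that staff would apply: no non-study cannabinoids in the prior 2 months or during the study. The three-month difference lies between a criterion and a recruitment description, and the description is ordinarily the narrower of the two. Its possible cost is a smaller pool to approach for a trial of 10; that cost cannot be sized from the protocol. There is no demonstrable effect on the rating-scale result.

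Two assumptions carry this conclusion. Screeners are assumed to read the cannabinoid item together with the nightly instruction to use the cream. Diagnosis is assumed not to precede the symptomatic course that the criterion counts. The second could fail for someone diagnosed long ago whose symptoms went away and returned less than three months before entry. Such a person would still be tested against the inclusion criterion, because the protocol requires subjects to meet all of the criteria.

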#### Abstract:

Anecdotally, we have preliminary observed 4-5 individuals with moderate to severe RLS describing near complete resolution of sensorimotor symptoms after consistently topically applying Chylobinoid™ cream to the affected extremities. We endeavor to validate these non-clinical observations by setting up a clinical trial with appropriate statistical power to demonstrate Chylobinoid's effectiveness of improving symptoms associated with RLS relative to placebo.

Our clinical endpoints will be measured using the International Restless Legs Syndrome Rating Scale

- 1. Statistically significant improvement of symptoms
- 2. A Minimally Clinically Important Difference of 3-point reduction.

We will present the data at selected scientific meetings and, depending on the results, will publish the study in a peer-reviewed journal.

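### Eligibility does not bar past users of the study cream, so a relapsed responder from the anecdotal group could be counted in the 10-person validation

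*Protocol*

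**What the plan says.** The Abstract states the origin of the trial: "we have preliminary observed 4-5 individuals with moderate to severe RLS describing near complete resolution of sensorimotor symptoms" after consistent use of the cream. It then says the trial is meant to validate these observations. The Significance section adds that the aim is to prove effectiveness in a clinical setting.

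Three rules bear on whether someone who has already used the cream can enter:

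- Exclusion criteria, last item: "No recent cannabinoid use in the last 2 months, and no use during the study". Read literally, this is a double negative inside a list of exclusions, and the study cream is itself a cannabinoid product. The evident intent is to exclude anyone who used a cannabinoid in the past 2 months and to forbid use outside the trial. That reading is used here.
- Exclusion criteria, allergy item: "Allergy to Cannabidiol (CBD) Cannabidiolic acid (CBDa), or any other ingredient contained in the topical cream". This is the only exclusion tied to the product's ingredients.
- Participants and protocols: "Anyone who does not meet the IRLS criteria for at least mild RLS with a minimum IRLS score of 7 will screen fail".

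The Inclusion criteria ask for "Patients with at least 3 month-course of symptomatic restless leg syndrome" and say nothing about earlier use of the product. The same holds for the recruitment sentence: "Participants with at least a three-month diagnosis of RLS without prior operative intervention will be approached for enrollment in the study". The phrase new participant questionnaires in that section names a form. It does not require that participants be new to the cream.

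The design is open-label with no control arm described. The outcome is a self-reported score taken by telephone and analysed as within-person change, and the size is fixed at "Sample Size: 10 participants".

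**The concern.** Validation needs data separate from the observation being validated. The people in the Abstract are known because they reported a good response, so they are selected on outcome. Any of them in the trial would partly re-measure the anecdote, and would come to an open-label study with a personal history of benefit.

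The trial has little to dilute this. Both primary outcomes, a statistically significant change and a 3-point change on the IRLS scale, come from one set of 10 change scores with no comparator. The group in the Abstract is 4-5 people, or 40-50% of 10 places if all of them entered. A reader of a positive result could not tell how much of it was new evidence.

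**Working it through.** **Who can pass the rules.** Take a person from the group in the Abstract.

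| Situation at screening | Rule that applies | Eligible? |
|---|---|---|
| Still using the cream, or used it in the past 2 months | 2-month cannabinoid look-back | No |
| Stopped more than 2 months ago, IRLS score below 7 | Minimum score of 7 | No |
| Stopped more than 2 months ago, relapsed to 7 or more | None | Yes, if the other criteria are met |

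Only the third row is open.

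**Effect on the mean change.** Inputs from the protocol are n = 10, a 3-point threshold and a minimum score of 7. The protocol gives no derivation of n = 10, so there is no figure to reproduce. If *k* past responders each fall by *r* points and nobody else changes, the expected mean fall is *k* × *r* / 10.

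- Fall needed from each to reach 3 points: *r* = 30 / *k*. For *k* = 4 this is 7.5; for *k* = 5 it is 6.0.
- Limit from the entry score: a person who enters at 7 can fall by at most 7. Four such people move the mean by at most 4 × 7 / 10 = 2.8, below the threshold. Five could move it by at most 5 × 7 / 10 = 3.5.
- With an assumed fall of 15 (range 12-18, not in the protocol), each person moves the mean by 1.5 (1.2-1.8). Two give 3.0 (2.4-3.6) and four give 6.0 (4.8-7.2). Such falls need entry scores of at least 12-18. The moderate to severe description in the Abstract makes that plausible, but scores on entry are unknown.

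**Chance of meeting each primary outcome.** Assumed: a 15-point fall in past responders, mean change 0 in everyone else, SD of change 5 or 7, two-sided alpha 0.05 (the protocol gives 0.05 without sidedness). The chance that the mean fall is 3 or more is Φ((1.5*k* − 3) / (SD/√10)). Significance was simulated with the protocol's sequence (Shapiro-Wilk, then paired t or Wilcoxon; 4,000 runs per case).

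| *k* | Mean fall of 3 or more | Significant improvement |
|---|---|---|
| 0 | 3-9% | about 3% |
| 1 | 17-25% | about 5% |
| 2 | 50% | 8-9% |
| 3 | 75-83% | 16-18% |
| 4 | 91-97% | 31-40% |
| 5 | 98-99.8% | 51-67% |

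Significance lags behind the mean because mixing responders with non-responders widens the spread. The mixture adds 225 × *k*(10 − *k*)/90 to the variance of the 10 scores. At SD 5:

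- *k* = 2: SD = √(25 + 40) = 8.06, so t is about 3.0 / (8.06/√10) = 1.18.
- *k* = 4: SD = √(25 + 60) = 9.22, so t is about 6.0 / (9.22/√10) = 2.06.
- *k* = 5: SD = √(25 + 62.5) = 9.35, so t is about 7.5 / (9.35/√10) = 2.54.

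The critical value on 9 degrees of freedom is 2.26.

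**Wider range.** With SD 4-8, falls of 10-20 points and the paired t-test alone, the chance of significance is 2-9% for one or two past responders, 19-54% for four and 28-90% for five.

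**The case against.** The strongest reply is that this is a contingency the protocol never describes. It does not say that any of the 4-5 people will be approached. To enter, such a person must have stopped a product that worked, stayed off all cannabinoids for more than 2 months and relapsed to a score of 7 or more. The protocol also says that criteria may not be waived. This stands, and it is why the point is conditional and minor.

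A reader might infer that nothing keeps the anecdotal responders out. The documents do not support that: the look-back and the score floor remove current users and those still in remission.

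A reader might also infer that one or two known responders could carry the trial. For significance they could not, at most about 9% under the assumptions above. Even with four, the test fails more often than it succeeds. For the 3-point mean their influence is larger, but only if their entry scores are well above 7.

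The calculation also sets the change in new participants to exactly zero, although an open-label design would probably produce some expectation response in them too. That makes the contrast starker than it would be in practice. The percentages illustrate sensitivity and are not a forecast.

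Nor can the harm be described as a result that no longer applies to untreated people with RLS, since the criteria never restrict enrolment to untreated people. Finally, without a control the study cannot separate a drug effect from expectation or natural fluctuation even in participants new to the cream. That limits what the fix achieves, but it does not make re-measuring the anecdote acceptable when the stated purpose is to validate it.

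**Conclusion.** The gap holds in a limited form. The criteria admit a past responder to this cream who stopped more than 2 months ago and relapsed, in a 10-person uncontrolled trial meant to validate what such people reported. Whether any will enrol is not stated.

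If some do, the 3-point criterion is the more exposed of the two primary outcomes: four people falling 7.5 points each are enough with no change in anyone else. Significance is affected little by one or two (at most about 9%) and materially only by four or five (about 31-67%). The head counts and the 7.5-point and 2.8-point bounds follow from the protocol's own numbers. The percentages rest on an assumed 15-point fall, an SD of 5-7 and no change in other participants. This is a cheap improvement of minor severity.

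**What to change.** Add to the Exclusion criteria: any previous use of Chylobinoid, in any form and at any time, including by the individuals described in the Abstract. Add a matching question to the new participant questionnaire. Keep the 2-month look-back for other cannabinoids.

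The cost is one exclusion line, one screening question and a loss from the recruitment pool that is probably small. The protocol does not say how many people have used the product, so the loss cannot be capped at the 4-5 in the Abstract. If the sponsor does not want to exclude past users, a weaker alternative is to record previous use at screening and report the results with and without those participants. With only 10 people, that second analysis could be very small.

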## Participants and protocols:

Participants of both genders will be recruited. Participants with at least a three-month diagnosis of RLS without prior operative intervention will be approached for enrollment in the study. Participants will be enrolled once the trial is described, questions answered, and consent form signed. Pre-treatment IRLSSG scores are collected over the phone on new participant questionnaires. Anyone who does not meet the IRLS criteria for at least mild RLS with a minimum IRLS score of 7 will screen fail. Participants will then have the trial cream described, how to apply it (see below), and then the cream will be mailed to them. Once received, participants will use the cream at least once a night to the affected area(s).

The topical cream will be contained in a jar. The cream will be applied by hand from a measuring spoon and massaged into the skin. The participant will measure 1 teaspoon and apply this amount to each of the regions of the area the participant reports having RLS. Participants will be instructed to apply the topical cream once per day 30-45 minutes before bed for a total duration of two weeks. Participants will be instructed to re-apply the cream if they wake up and feel RLS symptoms.

Participants will receive a follow up phone call at the end of the 2-week study. Post-treatment IRLSSG and the PGIC (patient's global impression of change) will be collected at that time. That completes the study.

Sample Size: 10 participants

## Primary outcome measure:

- 1. Statistically significant response to treatment using IRLSSG
- 2.A MCID of 3 using the IRLSSG

## **Secondary outcome measures:**

1. Patients Global Impression of Change (PGIC)

#### **Adverse Events**

As this is a topical application of cream that is not expected to get systemically absorbed, the chance of an adverse reaction is small. The participants will be instructed to perform a skin patch test prior to beginning the study. If there is any skin irritation, rash, itch or welts, the participant is instructed to wash the area with lukewarm water and soap and if needed apply Vaseline petroleum jelly or Aquaphor or its generics for comfort and to call the PI. If this occurs, the participant will not continue with the study.

Compensation: Participants will receive the trial cream free of charge.

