# A Pilot Study to Investigate the Benefits of a Cannabidiolic Acid Topical Cream for the Treatment of Restless Leg Syndrome

## **Synopsis:**

Restless Leg Syndrome (RLS) is multifactorial disease state with many different potential pathophysiological mechanisms, which includes dysfunctions from the cerebral cortex and spinal cord to mechanosensitive channels at the musculoskeletal periphery. Most therapeutic agents' effectiveness focuses on the CNS (e.g., dopaminergic drugs) or Renshaw cells. To our knowledge, therapeutic agents that are focused on the periphery were not very effective.

This technology focuses on the peripheral musculoskeletal component of the disease and is directed at treatment modalities that correct the dysfunction of mechanosensitive channels. By combining what is known about cannabinoids activity at the transient receptor potential channel of ankyrin 1 (TRPA1)² and the role TRPA1 plays in regulating the shape and rigidity of the surrounding membrane structure at the Piezo channels³, an effective therapy at the site of discomfort should emerge. Moreover, the lessening of membrane tension is imparted by molecules that readily penetrate the membrane⁴, which Chylobinoid, the topical active ingredient, is uniquely designed to do.

If successful, we will demonstrate, for the first time, an effective treatment for RLS with a topically applied medicine. This medicine will virtually eliminate the safety concerns associated with current RLS treatments. Moreover, to our knowledge, this potential medicine will represent the first time that mechanosensitive channels will be the target of a cannabinoid to treat a specific disease state.

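### The one planned post-treatment call lists no adverse-event question, so in the visible text harms are recorded only if participants volunteer them

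*Protocol*

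**What the plan says.** The design is stated as "Prospective open-label proof-of-concept trial" (Protocol, Research Methods), with "Sample Size: 10 participants" (Participants and protocols). The cream is mailed to participants, who use it nightly for two weeks on each affected region. Further use overnight is allowed: "Participants will be instructed to re-apply the cream if they wake up and feel RLS symptoms".

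The only planned contact after treatment is a phone call at two weeks. Participants and protocols says that post-treatment IRLSSG and PGIC "will be collected at that time. That completes the study". The primary and secondary outcome sections and the Statistical Analysis Plan section name no safety outcome or summary.

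Harms appear only in the Adverse Events section. It calls the chance of a reaction small, without a figure, and then says: "The participants will be instructed to perform a skin patch test prior to beginning the study". The next sentence lists skin signs and tells the participant to wash the area and, if needed, apply an ointment "for comfort and to call the PI. If this occurs, the participant will not continue with the study".

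The Synopsis says of the product: "This medicine will virtually eliminate the safety concerns associated with current RLS treatments".

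**The concern.** Which harms are asked about, of whom and when is decided in a protocol. A separate analysis plan cannot analyse answers that were never collected. Three features of the text matter here.

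- The single follow-up call has a stated content, and an adverse-event question is not part of it.
- The one stated reporting route starts with the participant, concerns skin signs only, and sits directly after the patch test. It may therefore not extend to the treatment weeks, when exposure is far greater than in a patch test.
- The text does not say whether a participant who starts and then stops the cream still receives the week-2 call. Those most likely to have had a reaction could be the ones nobody calls.

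At stake is the meaning of any later safety statement. The Abstract plans presentation at meetings and possible publication. A sentence that no adverse events were reported would then describe what participants chose to mention, and a reader could not tell this from a true absence of events.

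**Working it through.** **Step 1: the text side by side.**

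| Question | Participants and protocols | Adverse Events |
|---|---|---|
| Who starts the contact? | Study staff, at two weeks | The participant |
| What is covered? | IRLSSG, PGIC | Skin signs |
| When? | End of treatment | Patch test before the study; treatment weeks unclear |
| After stopping? | Not stated | Does not continue; week-2 call not addressed |

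Neither column gives a prompted question on harms, and neither gives a route for non-skin events. If the Adverse Events sentence covers only the patch test, the visible text has no on-treatment route at all. If it covers the whole study, the route is unprompted and limited to skin.

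**Step 2: what passive reporting could cost.** There is no figure in the Protocol to reproduce: the sample size of 10 has no stated derivation, and no event rate is given. Inputs:

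- n = 10 (Protocol, Participants and protocols).
- p = true proportion of participants with an on-treatment event. Assumed, from 1% to 30%.
- s = fraction of affected participants whose event is recorded. Assumed: 1 if everyone is asked and answers, 0.5 or 0.25 if events must be volunteered.

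With independent participants, all followed to week 2:

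P(at least one event recorded) = 1 − (1 − p·s)^10

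For example, at p = 0.10 and s = 0.5: 1 − 0.95^10 = 0.401.

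| p | s = 1 | s = 0.5 | s = 0.25 |
|---|---|---|---|
| 1% | 9.6% | 4.9% | 2.5% |
| 5% | 40.1% | 22.4% | 11.8% |
| 10% | 65.1% | 40.1% | 22.4% |
| 20% | 89.3% | 65.1% | 40.1% |
| 30% | 97.2% | 80.3% | 54.1% |

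The values of s below 1 presuppose that some participants do volunteer reports during treatment. They belong to the wider reading of the Adverse Events section, or to remarks made unprompted at the call. If nothing were volunteered, s would be 0 and no event would be recorded at any p.

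**Step 3: what asking everyone would and would not deliver.** With complete ascertainment and 0 events in 10, the exact two-sided 95% upper limit is 1 − 0.025^(1/10) = 30.8%. With 1 event in 10, the exact 95% interval is 0.3% to 44.5%. Asking makes the count interpretable, but ten participants still leave the rate very uncertain.

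**The case against.** **The argument is from silence.** The Protocol does not say that adverse events will go unrecorded, and consent and contact pages, which may carry reporting instructions, are not in the text at hand. This stands as a limit: the point concerns the visible text only, and a reader should not infer that the trial has no other reporting route. It does not remove the point, because the content of the week-2 call is spelled out and a contact instruction would still leave reporting to the participant.

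**The risk is small and this is a pilot.** At a 1% rate, ten participants would probably show no event even if all were asked (9.6% chance of any). That stands, and it is why low rates are in the table. But the small chance is an expectation without data, and in a group of 10 each missed event is a tenth of the sample.

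**The Synopsis sentence.** A reader might infer that the trial sets out to show better safety than current treatments. The documents do not support that. The sentence follows one that begins conditionally and concerns efficacy, no safety objective is declared, and no planned analysis is tied to it. What remains is wording that is too strong: there is no group on current treatments, so no planned data bear on the comparison.

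**The patch test.** Participants and protocols goes from receipt of the cream to nightly use without mentioning the patch test, and a reader might call that a contradiction. It is not one: a patch test on receipt, followed by nightly use, fits both sections.

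**The IRLS result.** A reader might also infer bias in the primary result from early stoppers. The documents give no basis for its size or direction, and none is claimed.

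**Conclusion.** The point holds for the visible text. The one planned post-treatment contact names no harms question, and the only stated route is an unprompted call about skin signs whose scope is unclear. On-treatment and non-skin events would be recorded only if volunteered.

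The size of the loss cannot be derived from the documents. The illustration rests on assumed rates, an assumed reporting fraction of one half, independence and full follow-up. Under these assumptions the chance of recording any event drops by about 18 percentage points at a 5% rate (40.1% − 22.4%), 25 at 10% (65.1% − 40.1%) and 24 at 20% (89.3% − 65.1%), but by under 5 at 1% (9.6% − 4.9%).

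The change should be made because it is cheap and decides whether a report of no events can be interpreted. The Synopsis wording is a minor matter beside it.

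**What to change.** 1. At the week-2 call, ask every participant who was mailed cream, including anyone who stopped early, a standard question on skin and other adverse events.
2. At the same call, seek IRLS and PGIC from those who started the cream and then stopped.
3. Report events and patch-test failures out of all who were mailed cream, with exact confidence intervals.
4. In the Adverse Events section, state whether the skin-sign sentence covers only the patch test or also the treatment period, and whether leaving the study also ends the week-2 call. Align Participants and protocols with the answer. The rule on stopping is left as it is; these changes concern data collection.
5. Soften the safety sentence in the Synopsis so that it does not compare the cream with current treatments.

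The cost is one or two questions in a call already planned, a few extra calls to early stoppers, and a wording amendment. The downside for the sponsor is a possibly less favourable safety statement.
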